9.3. Recording and Follow-Up of Adverse Events and/or Serious Adverse Events

Adverse Event and Serious Adverse Event Recording

- An AE/SAE that begins or worsens after informed consent is signed should be recorded on the Adverse Event Form in the eCRF. AEs/SAEs should be reported for enrolled participants, but only SAEs need to be reported for screen failure participants. For enrolled participants, conditions that were present at the time informed consent was given should be recorded on the Medical History eCRF. For detailed information refer to the eCRF guidelines.
- When an AE/SAE occurs, it is the responsibility of the investigator to review all documentation (eg, hospital progress notes, laboratory reports, and diagnostic reports) related to the event.
- The investigator (or delegate) will then record all relevant AE/SAE information in the eCRF.
- It is **not** acceptable for the investigator to send photocopies of the participant's medical records in lieu of completing the Adverse Event Form in the eCRF.
- There may be rare instances when copies of medical records for certain cases are requested. In this case, all participant identifiers, with the exception of the participant number, will be redacted by the site staff on the copies of the medical records before submission. These records can be submitted to Incyte Pharmacovigilance by email/fax per the contact information listed in the Study Reference Manual or as per SAE completing guidelines.
- The investigator will attempt to establish a diagnosis of the event based on signs, symptoms, and/or other clinical information. Whenever possible, the diagnosis (not the individual signs/symptoms) will be documented as the AE/SAE. When a clear diagnosis cannot be identified, each sign or symptom should be reported as a separate AE/SAE.

To the extent possible, each AE/SAE should be evaluated to determine the following:

- The severity grade (CTCAE v5.0 Grade 1 to 5). See below for further instructions on the assessment of intensity.
- Whether there is at least a reasonable possibility that the AE is related to the study drug: suspected (yes) or not suspected (no). See below for further instructions on the assessment of causality.
- The start and end dates, unless unresolved at the final safety follow-up visit.
- The action taken with regard to study drug as a result of the AE/SAE(s).
- The event outcome (eg, not recovered/not resolved, recovered/resolved, recovering/resolving, recovered/resolved with sequelae, fatal, unknown).
- The seriousness, as per the SAE definition provided in Section 9.2.
- The action taken with regard to the event. Note: If an AE is treated with a concomitant medication or nondrug therapy, this action should be recorded on the Adverse Event Form and the treatment should be specified on the appropriate eCRF (eg, Prior/Concomitant Medications, Procedures and Non-Drug Therapy).

Assessment of Intensity

The severity of AEs will be assessed using CTCAE v5.0 Grades 1 through 5. If an event is not classified by CTCAE, the severity of the AE will be graded according to the scale below to estimate the grade of severity.

The investigator will make an assessment of intensity for each AE and SAE reported during the study and assign it to 1 of the following categories:

- **Grade 1:** Mild; asymptomatic or mild symptoms; clinical or diagnostic observations only; treatment not indicated.
- **Grade 2:** Moderate; minimal, local, or noninvasive treatment indicated; limiting age-appropriate activities of daily living.
- **Grade 3:** Severe or medically significant but not immediately life-threatening; hospitalization or prolongation of hospitalization indicated; disabling; limiting self-care activities of daily living.
- Grade 4: Life-threatening consequences; urgent treatment indicated.
- Grade 5: Fatal.

Assessment of Causality

- The investigator is obligated to assess the relationship between study drug and each occurrence of each AE/SAE.
- A "reasonable possibility" of a relationship conveys that there are medical facts, evidence, and/or arguments to suggest a causal relationship, rather than that a relationship cannot be ruled out.
- The investigator will use clinical judgment to determine the possibility of a relationship.
- The investigator will also consult the RSI in the IB or Product Information for study drug, or marketed products, respectively, in making their assessment.
- Alternative causes, such as underlying or concurrent disease(s), concomitant therapy, and other risk factors, as well as the temporal relationship of the event to study drug administration, will be considered and investigated.
- For each AE/SAE, the investigator **must** document in the medical notes that they have reviewed the AE/SAE and have provided an assessment of causality.
- With regard to assessing causality of SAEs:
 - There may be situations in which an SAE has occurred and the investigator has minimal information to include in the initial report. However, the causality assessment is one of the criteria used when determining regulatory reporting requirements. Therefore, it is very important that the investigator always make an assessment of causality based on the available information for every event before the initial transmission of the SAE.
 - The investigator may change their opinion of causality in light of follow-up information and submit the updated causality assessment.

Follow-Up of Adverse Events and Serious Adverse Events

• The investigator is obligated to perform or arrange for the conduct of supplemental measurements and/or evaluations as medically indicated or as requested by the sponsor to elucidate the nature and/or causality of the AE or SAE as fully as possible. This may include additional laboratory tests or investigations, histopathological examinations, or consultation with other health care professionals.

- Once an AE is detected, it should be followed in the AE eCRFs until it has resolved or until it is judged to be permanent; assessment should be made at each visit (or more frequently if necessary) of any changes in severity, the suspected relationship to the study drug, the interventions required to treat the event, and the outcome.
- When the severity of an AE changes over time for a reporting period (eg, between visits), each change in severity will be reported as a separate AE.
- If a participant dies during participation in the study or during a recognized follow-up period, the investigator will provide the sponsor with a copy of any postmortem findings, including histopathology.
- Updated SAE information will be recorded in the originally completed eCRF and reported to Incyte Pharmacovigilance until resolution, stabilization, the event is otherwise explained, or the participant is lost to follow-up.
- Any updated SAE data (including SAEs being downgraded to nonserious) will be submitted to the sponsor (or designee) within 24 hours (immediately in Germany) of receipt of the information.

9.4. Reporting of Serious Adverse Events

Regardless of suspected causality (eg, relationship to study drug, or study procedures), all SAEs occurring after the participant has signed the ICF through the last safety visit or at least 30 to 35 days after the last dose of study drug must be reported to the sponsor (or designee) immediately, without undue delay but not later than within **24 hours** (immediately in Germany) of obtaining knowledge of its occurrence unless otherwise specified by the Protocol. The investigator will submit any updated SAE data to the sponsor (or designee) immediately, without undue delay but not later than within 24 hours (immediately in Germany) of it being available. For Japan: This information must also be reported immediately to the head of the study site.

Investigators are not obligated to actively seek SAE information after the safety follow-up visit or 30 to 35 days after the last dose of study drug. If the investigator learns of any SAE, including death, at any time during this period, and they consider the event to be reasonably related to the study drug or study participation, then the investigator must notify the sponsor (or designee) within 24 hours (immediately in Germany) of becoming aware of the event.

After the initial AE/SAE report, the investigator is required to proactively follow each participant at subsequent visits/contacts. All SAEs will be followed until resolution, stabilization, the event is otherwise explained, or the participant is lost to follow-up (as defined in Section 7.3).

Prompt notification by the investigator to the sponsor regarding an SAE is essential so that legal obligations and ethical responsibilities toward the safety of participants and the safety of a study drug under clinical investigation are met.

If the SAE is not documented in the RSI of the parsaclisib IB for the study drug (new occurrence) and is thought to be related to the study drug, the sponsor or its designee may urgently require further information from the investigator for expedited reporting to health authorities. The sponsor or its designee may need to issue an Investigator Notification to inform all investigators involved in any study with the same drug that this SAE has been reported. Suspected unexpected serious adverse reactions will be collected and reported to the competent authorities and relevant ethics committees in accordance with Directive 2001/20/EC or as per national regulatory requirements in participating countries. For Japan, the sponsor will report

suspected expected deaths and life-threatening events to the PMDA as per local regulatory requirements.

The sponsor has a legal responsibility to notify both the local regulatory authority and other regulatory agencies about the safety of a study drug under clinical investigation. The sponsor will comply with country-specific regulatory requirements relating to safety reporting to the regulatory authority, IRB/IEC, and investigators.

Investigator safety reports must be prepared for suspected unexpected serious adverse reactions according to local regulatory requirements and sponsor policy and forwarded to investigators as necessary.

An investigator who receives an investigator safety report describing an SAE or other specific safety information (eg, summary or listing of SAEs) from the sponsor will review and then file it along with the IB and will notify the IRB/IEC, if appropriate, according to local requirements.

Serious Adverse Event Reporting

- Information about all SAEs is collected and recorded on the Adverse Event Form in the eCRF.
- The investigator must report within 24 hours (immediately in Germany) of learning of its occurrence any SAE via the EDC system (primary method) or by completing the Serious Adverse Event Report Form in English (only if the EDC system is not available. The contact information for Incyte Pharmacovigilance by email/fax is listed in the Study Reference Manual.
- In circumstances where the EDC system is not accessible for reporting SAE information (initial and/or follow-up SAE information) to the sponsor within 24 hours (immediately in Germany), refer to the Incyte Reference Guide for Completing the Serious Adverse Report Form. Once the EDC system is functional, the SAE report should be retrospectively added to the EDC system and follow-up should be completed through the EDC. The original copy of the Serious Adverse Event Report Form and the email or facsimile confirmation sheet must be kept at the study site (refer to the Incyte Reference Guide for Completing the Serious Adverse Report Form or Study Reference Manual for details and for the email address or fax number).
- Follow-up information is also recorded in the eCRF and transmitted to Incyte Pharmacovigilance via the EDC system. The follow-up report should include information that was not provided previously, such as the outcome of the event, treatment provided, action taken with study drug because of the SAE (eg, dose reduced, interrupted, or discontinued), or participant disposition (eg, continued or withdrew from study participation). Each recurrence, complication, or progression of the original event should be reported as follow-up to that event, regardless of when it occurs.

9.5. Potential Drug-Induced Liver Injury

For information on management of potential Hy's Law cases, see Appendix D.

9.6. Events of Clinical Interest

An ECI is an AE (serious or nonserious) that Incyte wishes to document in an organized manner for monitoring or understanding. An ECI does not require rapid communication by an investigator to Incyte unless it meets criteria for rapid communication as an SAE (see Section 9.2). The ECIs include laboratory abnormalities and clinical AEs as follows:

- ALT \geq 5 × ULN
- AST \geq 5 × ULN
- Colitis
- Diarrhea \geq Grade 2
- Intestinal perforation
- Rash \geq Grade 2
- Exfoliative dermatitis
- Pneumonitis
- PJP
- CMV infection
- Herpes simplex
- Varicella zoster virus infection

9.6.1. Adverse Events of Special Interest

Not applicable.

9.7. Emergency Unblinding of Treatment Assignment

In case of a medical emergency, for a participant's safety management, the procedure for emergency unblinding is provided to the investigator in the IRT Manual. The investigator has the primary right to break the blind to treat a participant in emergency circumstances.

If a participant's treatment assignment is unblinded, the sponsor or its designee should be notified immediately by telephone for awareness.

If an investigator, the site personnel performing assessments, or a participant is unblinded, then the participant must discontinue study drug unless there are ethical reasons to have the participant remain on the study treatment. In these cases, the investigator must obtain specific approval from the sponsor's (or its designee's) medical monitor for the participant to continue in the study.

9.8. Pregnancy

Pregnancy, in and of itself, is not regarded as an AE unless there is suspicion that the study drug may have interfered with the effectiveness of a contraceptive medication or method. When a pregnancy has been confirmed in a participant during maternal or paternal exposure to study drug, the following procedures should be followed in order to ensure safety:

- The study drug must be discontinued immediately (female participants only).
- The investigator must complete and submit the Incyte Clinical Trial Pregnancy Form to the sponsor or its designee within **24 hours** of learning of the pregnancy.

Data on fetal outcome are collected for regulatory reporting and drug safety evaluation. Follow-up should be conducted for each pregnancy to determine outcome, including spontaneous or voluntary termination, details of the birth, and the presence or absence of any birth defects, congenital abnormalities, or maternal and/or newborn complications, by following until the first well-baby visit. Pregnancy should be recorded on a Clinical Trial Pregnancy Form and reported by the investigator to the sponsor or its designee. Pregnancy follow-up information should be recorded on the same form and should include an assessment of the possible causal relationship to the sponsor's study drug to any pregnancy outcome, as well as follow-up to the first well-baby visit or the duration specified in local regulations, whichever is later. Refer to the Incyte Reference Guide for Completing the Clinical Trial Pregnancy Form or Study Reference Manual for further details.

Any SAE occurring during pregnancy of a study participant must be recorded and reported as described in Section 9.4.

Abnormal pregnancy outcomes (eg, spontaneous abortion, fetal death, stillbirth, congenital anomalies, or ectopic pregnancy) are considered SAEs (if occurring in the study participant) and must be reported as described in Section 9.4. If an abnormal pregnancy outcome is reported in a study participant's partner, the event should be reported to the sponsor on the Clinical Trial Pregnancy Form.

9.9. Warnings and Precautions

Special warnings or precautions for the study drug, derived from safety information collected by the sponsor or its designee, are presented in the IB. Additional safety information collected between IB updates will be communicated in the form of Investigator Notifications. Any important new safety information should be discussed with the participant during the study as necessary. If new significant risks are identified, they will be added to the ICF.

9.10. Product Complaints

The sponsor collects product complaints on study drugs and drug delivery systems used in clinical studies in order to ensure the safety of study participants, monitor quality, and facilitate process and product improvements.

All product complaints associated with material packaged, labeled, and released by the sponsor or its designee will be reported to the sponsor. All product complaints associated with other study material will be reported directly to the respective manufacturer.

The investigator or their designee is responsible for reporting a complete description of the product complaint via email or other written communication to the sponsor contact or respective manufacturer as noted in the packaging information. Any AE associated with a product complaint should be recorded as described in Section 9.3.

If the investigator is asked to return the product for investigation, they will return a copy of the product complaint communication with the product.

For Japan, complaints associated with unapproved medical devices will be reported to the sponsor with a Medical Device Defect Report Form, and the sponsor will report medical device defects to the PMDA as per local regulatory requirements.

9.11. Treatment of Overdose

Overdose is not an SAE unless it meets the criteria of an SAE (see Section 9.2).

For this study, any daily dose of study drug greater than 2.5 mg during the study within a 24-hour time period (\pm 4 hours) will be considered an overdose and recorded in the eCRF.

Incyte does not recommend specific treatment for an overdose. Overdose with concomitant medication treatment will not be recorded in the eCRFs unless it resulted in an AE.

In the event of an overdose, the investigator should do the following:

- Contact the medical monitor immediately.
- Closely monitor the participant for any AE/SAE and laboratory abnormalities until study drug can no longer be detected systemically (at least 3 days).
- Document the quantity of the excess dose as well as the duration of the overdose in the eCRF.

Decisions regarding dose interruptions or modifications will be made by the investigator in consultation with the medical monitor based on the clinical evaluation of the participant. Treatment of overdose should consist of general supportive measures.

10. STATISTICS

Note: Upon implementation of Protocol Amendment 2, enrollment has been closed and protocol-required procedures have been reduced for ongoing participants. With limited participants enrolled in each treatment group and the option for early cross-over to parsaclisib, most of the statistical analyses defined by the protocol are not applicable. Therefore, the final analyses to accommodate those changes will be specified in the Statistical Analysis Plan.

10.1. Sample Size Determination

Approximately 100 participants will be randomized 2:1 (approximately 67:33) to parsaclisib 2.5 mg QD or matching placebo using a fixed block size within each stratum. For the statistical comparison on the binary primary efficacy endpoint, the sample size calculation is based on a Chi-square test.

Based on the results of the Phase 2 study (INCB 50465-206), the response rate for the primary endpoint is assumed to be 70% for parsaclisib 2.5 mg. With limited data, such response rates in the placebo group are not reported in historical studies. The response rate for placebo group can only be assumed to around 25% from the literature review (Barcellini et al 2014, Birgens et al 2013, Lechner and Jäger 2010). Based on these assumptions, the sample size of 100 will provide enough power (over 90%) to detect such a difference with a 2-sided alpha of 0.05.

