2.2.2. Justification for Dose

Parsaclisib 2.5 mg QD or matching placebo will be self-administered for 24 weeks, followed by continued treatment with parsaclisib QD in the open-label period for up to 24 weeks and in the long-term extension.

In study INCB 50465-206, exploration of parsaclisib dose in AIHA participants resulted in a determination of 2.5 mg QD as the recommended dose.

In Cohort 1 (N = 10), all participants were initially treated with parsaclisib 1.0 mg QD. Based on insufficient hemoglobin response by Week 6, 8 of the 10 enrolled participants had their dose increased to 2.5 mg QD at Week 6 (1 participant remained on 1.0 mg and 1 participant discontinued before Week 6).

In Cohort 2 (N = 15), all participants were treated with parsaclisib 2.5 mg QD for 12 weeks.

During the course of the study, 7 out of 21 (33.3%) participants (N = 2 Cohort 1, N = 5 for Cohort 2) achieved a complete response (hemoglobin \geq 12 g/dL) at any visit from Week 6 to Week 12. Fourteen of 21 (66.7%) participants (N = 6 Cohort 1, N = 8 Cohort 2) achieved a partial response (defined as a hemoglobin of \geq 10 g/dL or a \geq 2 g/dL increase from baseline). Mean increases in hemoglobin were seen at Week 2 and continued to increase through Week 12 with Cohort 2 achieving a higher mean increase of 2.4 g/dL compared with 1.3 g/dL in Cohort 1 at Week 12. Overall, the dose of parsaclisib 2.5 mg QD is generally well—tolerated (refer to parsaclisib IB). The dose of 2.5 mg is proposed to provide sufficient exposure (estimated to be approximately 1 × IC₉₀ at trough) to maintain PI3K pathway inhibition while minimizing the frequency of late-onset AEs that may lead to study treatment withdrawal. Higher doses of parsaclisib have been explored in the oncology program (up to 45 mg QD). In oncology patients, higher rates of AEs were observed at doses above 5 mg per day.

If there are any intolerable AEs or hemoglobin in the high end of normal range in individual participants who receive 2.5 mg QD of study treatment, the dose should be decreased to 1 mg QD (see Section 6.5).

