3. OBJECTIVES AND ENDPOINTS

Table 6 presents the objectives and endpoints.

Table 6: Objectives and Endpoints

Objectives	Endpoints
Primary	
To evaluate the efficacy of parsaclisib in the treatment of participants with wAIHA.	Proportion of participants attaining a durable hemoglobin response, defined as hemoglobin ≥ 10 g/dL with an increase from baseline of ≥ 2 g/dL not attributed to rescue therapy at ≥ 3 of the 4 available visits at Week 12 and/or later during the 24-week double-blind treatment period.
Key Secondary	
To further evaluate the efficacy of parsaclisib in the treatment of participants with wAIHA.	• Proportion of participants with a ≥ 3-point increase from baseline in FACIT-F score at Week 24.
Other Secondary	
To further evaluate the efficacy of parsaclisib in the treatment of participants with wAIHA.	• Proportion of participants with a 50 m increase from baseline to Week 24 in a 6MWT.
	Change and percent change from baseline in FACIT-F score at each postbaseline visit.
	Change and percentage change from baseline in hemoglobin at each postbaseline visit.
	• Proportion of participants who received transfusions from Week 6 to Week 24 and from Week 24 to Week 48.
	Change and percentage change from baseline in daily corticosteroid dose at Week 24.
	• Proportion of participants who required rescue therapy at any visit from Week 6 through Week 24, and from Week 24 to Week 48.
To evaluate the safety and tolerability of parsaclisib in participants with wAIHA.	• Frequency and severity of AEs, including the evaluation of clinical laboratory results, vital signs, ECGs, and the results of physical examinations.

Table 6: Objectives and Endpoints (Continued)

Objectives	Endpoints

Table 6: Objectives and Endpoints (Continued)

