### **3.3. Sample Size Consideration**

Approximately 100 participants will be randomized 2:1 (approximately 67:33) to receive either parsaclisib 2.5 mg QD or matching placebo using a fixed block size within each stratum. For the statistical comparison on the binary primary efficacy endpoint, the sample size calculation will be based on a Chi-square test.

Based on the results of the Phase 2 study (INCB 50465-206), the response rate for the primary endpoint is assumed to be 70% for parsaclisib 2.5 mg QD. With limited data, such response rates in the placebo group are not reported in historical studies. The response rate for the placebo group can only be assumed to around 25% from the literature reviewed ([Barcellini et al 2014](#), [Birgens et al 2013](#), [Lechner and Jäger 2010](#)). Based on these assumptions, the sample size of 100 will provide enough power (over 90%) to detect such a difference with a 2-sided alpha of 0.05.

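### Is the power claim undermined because the 70% parsaclisib response rate credited to Phase 2 does not match the Phase 2 figures shown?

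*Protocol*

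**What the plan says.** Protocol 10.1 plans a 2:1 randomization: "Approximately 100 participants will be randomized 2:1 (approximately 67:33"). It sizes the trial on a chi-square test at two-sided 0.05. The parsaclisib rate is introduced with "Based on the results of the Phase 2 study (INCB 50465-206), the response rate for the primary endpoint is assumed to be 70" per cent. The placebo rate is put at around 25% from literature, with the remark that such rates are not reported in historical studies. SAP 3.3 repeats the reasoning and ends: "the sample size of 100 will provide enough power (over 90%) to detect such a difference".

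The primary endpoint (Protocol 3 and 10.3.1) requires hemoglobin of at least 10 g/dL together with a rise of at least 2 g/dL, not due to rescue, "at ≥ 3 of the 4 available visits at Week 12 and/or later during the 24-week double-blind treatment period". Continued rescue after Week 6, or two or more missing values among the four visits, makes a participant a nonresponder.

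Protocol 2.2.2 gives two Phase 2 rates. Complete response (hemoglobin of at least 12 g/dL at any visit in Weeks 6 to 12) was 7 of 21, or 33.3%. The other is "Fourteen of 21 (66.7%) participants (N = 6 Cohort 1, N = 8 Cohort 2) achieved a partial response", where either hemoglobin of at least 10 g/dL or a rise of at least 2 g/dL was enough. Cohort 1 started at 1.0 mg; Cohort 2 received 2.5 mg for 12 weeks.

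**The concern.** The planning rate is higher than the most generous overall Phase 2 rate on the page, yet it is applied to an endpoint that looks stricter. Two criteria must be met instead of either one, at three of four visits, with rescue and missing data counted against the participant. The Phase 2 figure also pools a cohort that started at a lower dose. If the true durable rate were well under 70%, a reader of Protocol 10.1 or SAP 3.3 would think the trial better powered than it was. Later planners might also reuse 70% as a Phase 2 result for this endpoint.

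**Working it through.** **Inputs.** Protocol 10.1: n1 = 67, n2 = 33, p2 = 0.25, two-sided alpha 0.05, chi-square test. Protocol 2.2.2: 14/21 = 0.667.

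**Formula (pooled variance under the null).**
- p̄ = (67·p1 + 33·p2)/100
- SE0 = √[p̄(1 − p̄)(1/67 + 1/33)]
- SE1 = √[p1(1 − p1)/67 + p2(1 − p2)/33]
- power = Φ[(p1 − p2 − 1.96·SE0)/SE1]

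**The plan's own figure.** With p1 = 0.70: p̄ = (46.9 + 8.25)/100 = 0.5515, SE0 = 0.1058, SE1 = 0.0939. Then z = (0.45 − 0.2074)/0.0939 = 2.58 and power = 99.5%. Exact enumeration of the chi-square test gives 99.3%, and the Fisher exact test 99.0%. The claim of over 90% is reproduced with room to spare.

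**Using the Phase 2 figure instead.** With p1 = 0.667: p̄ = 0.529, SE0 = 0.1062, SE1 = 0.0949, z = 2.20 and power = 98.6%. The gap between 70% and 66.7% is immaterial.

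**Break-even.** With placebo held at 25%:

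| Parsaclisib rate | Power |
|---|---|
| 60% | 93% |
| 58.2% | 90% |
| 55% | 83% |
| 53.3% | 78% |
| 50% | 68% |
| 40% | 31% |

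The margin below 70% is about 12 points. With a continuity correction the break-even is 60.5%.

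**Diluting both arms.** The table lowers only the parsaclisib rate, but the stricter endpoint binds both arms. At 50% vs 20% power is 85%; at 50% vs 15% it is 95%; at 45% vs 15% it is 88%; at 40% vs 15% it is 74%.

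A rough model shows how much this matters. Assume four exchangeable visits per participant, beta-binomial with within-participant correlation ρ. Read 66.7% and 25% as the chance of responding at one or more visits, then compute the chance of responding at three or more. All of this is assumption; the documents give no visit-level data.

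| ρ | Parsaclisib, 3 of 4 | Placebo, 3 of 4 | Power, placebo fixed at 25% | Power, both diluted |
|---|---|---|---|---|
| 0.5 | 36% | 9% | 20% | 88% |
| 0.7 | 49% | 14% | 65% | 96% |
| 0.8 | 55% | 17% | 84% | 97% |

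The large loss of power comes almost entirely from leaving placebo at 25%.

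**What the Phase 2 data allow.** The exact 95% interval for 14/21 is 43% to 85%, which includes both 58% and 70%. Cohort 2 had 8 responders. Its evaluable number is not stated, but 21 evaluable in all with at most 10 from Cohort 1 puts it between 11 and 15, so its rate lies between 8/15 = 53.3% and 8/11 = 72.7%. That range also contains 70%.

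**The case for a change.** The strongest case for a change is that the text credits Phase 2 with a rate for the primary endpoint, and no number in either document bears that out. For the same participants at the same visits, each added requirement can only reduce the count of responders. Some readings of the Phase 2 data fall below the break-even even on the looser definition: 14/25 = 56% if the four participants outside the 21 counted as failures (power 85%), or 8/15 (78%). The offset from a lower placebo rate is uncertain, and the SAP dated 17 January 2024, after the decision to terminate, still carries the sentence.

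The missing derivation stands; the inference that the durable rate must be lower does not follow. The Phase 3 visits fall in Weeks 12 to 24, whereas the Phase 2 complete response is counted in Weeks 6 to 12. Protocol 2.2.2 says mean hemoglobin was still rising at Week 12. Phase 2 also enrolled cold agglutinin and mixed-type disease (Protocol 2), while Phase 3 is confined to primary warm disease, and the effect of that on the rate is unknown. Treatment in Phase 2 ran up to 585 days (Protocol 2.2), so the sponsor may hold a durable rate that is not printed here. Both documents call 70% assumed and state the power as conditional on that.

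**Conclusion.** The point is fair as an observation: the documents do not show where a 70% durable rate comes from. It does not show the power claim to be wrong. The figure is correct on its stated inputs (99.5%), survives substitution of the Phase 2 rate (98.6%), and holds down to about 58% with placebo at 25%. The much lower figures depend on diluting one arm only.

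No decision now turns on it. Enrollment closed with 12 participants randomized according to Protocol 2.2, or 13 according to SAP 1. The note opening Protocol 10 says most planned analyses no longer apply, and SAP 7 and 11.1 provide no p-values or comparisons. Relabelling the 70% or adding a power range would leave every result and conclusion of this trial as it is. This is missing detail about a planning assumption, and no change to the plan follows.

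The conclusion rests on the 67:33 allocation and on reading 25% as a planning value as uncertain as the 70%. The two-arm comparison also rests on the illustrative visit-correlation model.
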